4.1 Description of Study Design

This is a pilot, proof of concept, placebo-controlled, parallel study. Participants will be recruited from NYU Langone Medical Center's ENT Department and will receive either high-dose intranasal oxytocin or the placebo, a nasal spray containing the same inactive ingredients as the active drug: magnesium chloride crystals, citric acid anhydrous gran., sodium citrate powder, sterile water for irrigation, and Pcca Mucolox liquid base to replicate the feel and consistency of the oxytocin nasal spray. When changing the compounding pharmacy, we conducted a blinded test of placebo formulations. We found that the placebo containing all of the inactive ingredients as the active oxytocin nasal spray was a significantly better match in consistency to the active drug, as compared to distilled water and Pcca Mucolox. The primary outcome measure for this study will be a greater than 50% improvement in tinnitus loudness on the Visual Analog Scale (VAS). The secondary outcome measure will be improvement (p < 0.10) in the Tinnitus Handicap Inventory Severity Scale (THI)/Clinical Global Impression Scale (CGI) and Tinnitus Functional Index (TFI) (26, 27, 28). The metrics on the secondary endpoints are exploratory only and as such we will not look for specific changes. These results will guide us in the next, larger study.

The study will consist of 3 phases:

- 1. A 1 week baseline phase during which time we will track daily tinnitus loudness on VAS using a study log. Patients will not receive any study drug during this phase. No changes in any concomitant medications will be allowed during this phase. In addition, the use of dinoprostone or ephedrine is not permitted throughout the study.
- 2. A 9 week non-blinded phase is which all patients will receive the oxytocin nasal spray 4 times daily. All patients will begin at a dose of 30 IU 4 times daily for 2 weeks; If no response is reported (defined as a decrease in VAS of < 2), they will have the dose increase by 5 IU per spray every 2 weeks, until a maximum dose of 45 IU 4 times daily. If patients report improvement (defined as improvement in VAS >3) at any dose, they will remain at that dose through the end of the second phase. In the event that the patient experiences a moderate side effect, the dose will be decreased to the previous dose for the remainder of this phase.

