5.7 Participant Withdrawal or Termination

5.7.1.1 Reasons for Withdrawal or Termination

Participants are free to withdraw from participation in the study at any time upon request. An investigator may terminate participation in the study if:

- Any clinical adverse event (AE) or other medical condition or situation occurs such that continued participation in the study would not be in the best interest of the participant
- The participant meets an exclusion criterion (either newly developed or not previously recognized) that precludes further study participation
- At any point during the study, a subject is found to have abnormal urine sodium or osmolality levels or an abnormal comprehensive metabolic panel
- They experience a significant rise in blood pressure (>150/100) or intolerable side effects (nausea, vomiting, headache, or significant worsening of tinnitus)

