6.1.5 Dosing and Administration

After the baseline period of the study (1 week), subjects will receive intranasal oxytocin for 9 weeks. They will receive a spray bottle with study medication at Visit 3 to be self-administered at home four times per day (9AM, 1PM, 5PM, and 9PM). They will be instructed to apply 1 puff (the equivalent of 30 to 45 oxytocin IU) in one nostril four times per day, equivalent to 120 to 180 IU per day.

Subjects will be shown the proper way to use the nasal spray and administer the study medication. With their head facing forward, not tilted up or down, they should place the sprayer in one nostril and spray once while holding their breath. They should then pinch both nostrils closed for 5 seconds. They will be instructed not to sniff in or blow their nose for at least 5 minutes after administration. During the following 6 weeks of the study, subjects may receive placebo or oxytocin nasal spray. The placebo will be administered in the same manner as the active study drug, with 1 puff in one nostril four times per day (9AM, 1PM, 5PM, and 9PM). If the subject is randomized to the active drug during this phase, their dose will be the same dose they received during Week 9 of the study, during the non-blinded phase.

The nasal spray should be refrigerated when not being used. Subjects will also have a re-freezable bag to store their spray bottles in when not near a refrigerator.

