9.3 Analysis Datasets

Efficacy data will be analyzed for all subjects who received at least one dose of study-drug and provided at least one endpoint measurement during the non-blinded study phase. For the blinded study phase efficacy data will similarly be analyzed for all randomized patients providing at least one endpoint measurement. A separate per protocol patient population defined as patients providing complete efficacy data will also be defined for each study phase.

Safety and tolerability data will be analyzed for all enrolled patients receiving at least one dose of studydrug during the non-blinded study phase and then for all randomized participants during the blinded study phase.

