9.4 Description of Statistical Methods

Data from this pilot study will be summarized separately for the non-blinded study phase and by study arm for the blinded study phases. The area under the VAS curve after subtracting baseline value will be determined using the linear trapezoidal method. These areas will be determined for the efficacy population using the last observation carried forward (LOCF). The mean and standard deviation for the non-blinded phase will be determined and the effect size for the mean area from zero calculated. For the blinded phase week 3 (after a 2 week "washout") will serve as the baseline and the area under the VAS curve from baseline will be calculated using LOCF imputation for missing post baseline data. To avoid potential cross-over effects from the 9 week non-blinded phase when all subjects receive active drug, after randomization, subjects will receive either active drug or placebo. The first 2 weeks of this 6 week period will be a washout period from statistical analysis. While subjects will still receive study drug, data collection for that phase will not begin until week 3 of that 6 week period. The mean and standard deviation in area under the VAS curve from baseline for each study arm will be determined and the partial eta effect size for the mean difference between study arms calculated. This summary will be performed for the per protocol study population as well to investigate the relative influence of missing data on the effect size determination.

Frequencies and percentages for the secondary safety and tolerability endpoints will be determined using the ITT patient population for the non-blinded study phase and all randomized participants during the nonblinded study phase. The other secondary endpoint, incidence of the change in THI of 1 point or greater, will be summarized by study arm for those participants providing at least 1 post-week 3 baseline THI measurement.

The analyses will be refined and adjusted in anticipation of study termination and data lock.

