9.4.2 Analysis of the Primary Efficacy Endpoint(s)

The primary efficacy endpoint is the area under the VAS curve from baseline for all randomized participants during the blinded study phase. The week 3 data after two week washout will serve as the baseline and the interval/ratio scaled area determined using the linear trapezoidal method. The expectation is that placebo participants' post-baseline VAS data will remain relatively consistent with baseline values while active treatment will trend post-baseline. Using an LOCF imputation strategy is therefore a conservative strategy for handling missing data by understating trending in the active treatment group without introducing trending in the placebo group. The mean and standard deviation by study arm in the area under the VAS curve from baseline will be presented along with the partial eta squared effect size estimate for the mean difference between study arms. The availability of data will be determined by study arm at each post-baseline study time point during the blinded study phase to investigate the potential influence of missing data. A per-protocol analysis will also be presented to further investigate the influence of missing data on the primary efficacy endpoint.

The area under the VAS curve from baseline will similarly be determined and analyzed separately for the open label/non-blinded study phase. Since this measure is biased by participant knowledge of treatment the effect size of the mean VAS area from baseline will be determined and cautiously interpreted.

As included in Section 9.1, the effect size will be calculated and interpreted using η^2 =0.2 as a small effect, η^2 =0.5 as a medium effect, and η^2 =0.8 as a large effect (20). These cut-offs will be used to judge the strength of the treatment relative to placebo control with medium ($\eta^2 \ge 0.5$) considered a treatment "success."

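### Calling LOCF conservative for the primary AUC is unsupported in this design: with unequal or outcome-related dropout it can bias the arm difference in either direction

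*Combined protocol and SAP*

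**What the plan says.** Section 9.4 sets the rule for the blinded phase: "the area under the VAS curve from baseline will be calculated using LOCF imputation for missing post baseline data". The baseline is blinded week 3, after two weeks on randomized treatment that are left out of the analysis, and the area runs to blinded week 6 (Sections 4.2.1.1 and 9.2).

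Section 9.4.2 gives the reason for LOCF: "The expectation is that placebo participants' post-baseline VAS data will remain relatively consistent with baseline values while active treatment will trend post-baseline". From this it concludes: "Using an LOCF imputation strategy is therefore a conservative strategy for handling missing data by understating trending in the active treatment group". It adds that LOCF brings no trend into the placebo group.

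Other sections bear on that reasoning:

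- Section 4.1: "A 9 week non-blinded phase is which all patients will receive the oxytocin nasal spray 4 times daily".
- Section 6.1.5, for those randomized to active: "their dose will be the same dose they received during Week 9 of the study".
- Section 3: the comparison group starts on active drug and is switched to placebo.
- Section 5.7.1.1: an investigator may end participation for intolerable side effects, which include "significant worsening of tinnitus".
- Section 6.1.8: urine sodium or osmolality abnormalities lead to discontinuation and withdrawal.
- Section 9.3: the blinded-phase efficacy set is "all randomized patients providing at least one endpoint measurement".

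The plan also includes checks. Section 9.4.2 tabulates data availability by arm and time point and adds a per-protocol analysis. Sections 9.4.3 and 9.4.5 summarize withdrawals by time point, arm and reason.

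**The concern.** LOCF has no general property of being conservative. Its effect depends on the trajectory in each arm, on who leaves, and on why they leave. The plan derives the property from one assumed pair of trajectories, for which it cites no data. In a design where both arms arrive on active drug and only one is switched, there is no evident reason to expect the unchanged arm to move and the switched arm to hold still.

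The withdrawal rules add to this. One ground for termination is close to the outcome itself, and another may be related to the drug. A carried-forward value may therefore be selected by outcome or by treatment.

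The arm difference in AUC is converted to partial eta squared. That figure is compared with a success threshold (Section 9.4.2) and is meant to power the next study (Sections 9.2 and 9.5). A reader told that the missing-data method is conservative will treat the estimate as a floor, and the design does not justify doing so.

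**Working it through.** The documents give no figure for LOCF bias, blinded-phase dropout, VAS SD or trajectory, so there is no plan figure to reproduce. The enrolment allowance (50 to 30, so 20/50 = 40% loss) includes screen failures and is not split by arm or phase.

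**Assumptions.** One VAS value per week at blinded weeks 3, 4, 5 and 6; dropouts have their last value at week 4; the slopes and dropout rates below. Higher VAS is worse, so a positive placebo-minus-active difference favours the drug.

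**Formula.** With z the change from week 3 (z3 = 0), the trapezoid gives AUC = z4 + z5 + 0.5·z6.

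- Slope of 1 point per week, full data: 1 + 2 + 1.5 = 4.5.
- LOCF with last value at week 4: 1 + 1 + 0.5 = 2.5. Last value at week 5: 1 + 2 + 1 = 4.0. Last value at week 3: 0.

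**1. The plan's expectation (active −1 per week, placebo flat).** Each active dropout loses 4.5 − 2.5 = 2.0. With dropout of 10/20/40% in each arm, the true 4.50 becomes 4.50 − 2.0 × rate = 4.30/4.10/3.70.

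**2. Exact reversal (active flat, placebo +1 per week).** The same arithmetic applies to placebo: 4.30/4.10/3.70. With unequal dropout the result ranges from 3.70 to 4.50 and is never inflated.

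**3. Both arms flat.** No bias in the mean difference.

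**4. Both arms +1 per week, no true effect.** At 40% active and 10% placebo dropout:

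- Active: 0.6 × 4.5 + 0.4 × 2.5 = 3.70.
- Placebo: 0.9 × 4.5 + 0.1 × 2.5 = 4.30.
- Difference: +0.60 where the truth is 0. Swapping the rates gives −0.60.

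**5. Active +0.5, placebo +1 per week (true difference 4.50 − 2.25 = 2.25).** At 40%/10% active/placebo dropout, 4.30 − 1.85 = 2.45 (+9%). At 10%/40%, 3.70 − 2.15 = 1.55 (−31%).

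**6. Placebo participants leave at a transient peak.** Leavers follow 0, 3, 1, 1 (true AUC 4.5; LOCF 3 + 3 + 1.5 = 7.5). Other placebo participants follow 0, 1, 1, 1 (AUC 2.5). Active is flat.

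| Placebo dropout | True difference | LOCF difference | Inflation |
|---|---|---|---|
| 10% | 2.70 | 3.00 | 11% |
| 20% | 2.90 | 3.50 | 21% |
| 40% | 3.30 | 4.50 | 36% |

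**7. A milder form of 6, by simulation** (15 per arm, 20,000 runs, three assumed SD sets). Placebo steps up by 1 point, and anyone whose noisy week-4 change exceeds 1.5 or 2 leaves. The difference rises from about 2.5 to between 2.54 and 2.62, an inflation of 2% to 5%.

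**8. Effect on eta squared, same simulations.** For cases 1 and 2 at 0.5 points per week and 20% dropout, mean eta squared falls from 0.27/0.12/0.08 to 0.23/0.10/0.07 across the three SD sets. For case 4 at 0.5 points per week and 40%/10% dropout, it moves from 0.034–0.035 to 0.035–0.040. With n = 30 and no effect its expected value is already 1/29 = 0.034.

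**Baseline-only participants.** If the week-3 reading counts as an endpoint measurement under Section 9.3, LOCF sets every later change to zero and the AUC is 0. For the THI endpoint, Sections 9.4 and 9.4.3 require a value after week 3. The primary endpoint has no such condition.

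**The case against.** A reader might infer that the design reverses the plan's trends, so that placebo must rise while active stays flat. The documents do not establish that. Baseline comes after two weeks on randomized treatment, and Section 2.1 gives a plasma half-life of 3 to 17 minutes, so any relapse may be complete by then and placebo may be flat as the plan expects. Under Section 6.1.7, three two-week steps take a participant from 30 to 45 IU, so some reach their final dose only about two weeks before randomization. Some residual active trend cannot be excluded.

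A reader might also infer that reversal alone makes LOCF favour the drug. Cases 1 and 2 show that it does not: a clean reversal attenuates the difference exactly as the plan's own scenario does. Upward bias needs trends in both arms with unequal dropout, or informative dropout.

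The inputs are assumed, and the profile in case 6 is deliberately sharp; case 7 gives much less. Section 5.7.1.1 says that participation may be ended, so outcome-related selection is possible, not certain. Scoring a baseline-only participant as 0 is one reading of Section 9.3, not a stated rule. Replacement of withdrawals (Section 5.7.2) leaves the amount of missing data unclear.

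The planned availability table, withdrawal summaries and per-protocol analysis are real mitigation, but partial. Section 9.3 defines per protocol as complete efficacy data. Completers are themselves selected by dropout, so agreement with LOCF would not validate LOCF.

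**Conclusion.** The concern holds in this form: the conservative label is unsupported, and LOCF may bias the primary AUC difference either way when both arms trend with unequal dropout, or when dropout depends on outcome or drug. Under the stated assumptions the bias is ±0.60 point-weeks with no true effect, −31% to +9% with unequal slopes, and +11% to +36% for a carried-forward peak, or +2% to +5% in the milder simulation. The direction and size in this trial cannot be known from the documents.

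A reader might infer that LOCF could by itself produce a false success. The calculations do not support that. With equal arms, eta squared = d²/(d² + 4), so the 0.5 threshold corresponds to d = 2, and the shared-trend simulation moved mean eta squared by at most about 0.005. What is at stake is the estimate carried to the next study and the assurance attached to it. The point should be corrected before data lock. Confidence is moderate, because the trajectories and dropout pattern are unknown.

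**What to change.** 1. Delete the statement in Section 9.4.2 that LOCF is conservative, with the trend expectation that supports it.
2. Make the primary missing-data method a likelihood-based repeated-measures model, or multiple imputation, on weekly VAS from the daily log already collected (Sections 6.1.10 and 6.2). Derive the week 3 to 6 AUC contrast from it.
3. Keep LOCF and the completers analysis as sensitivity analyses. Add a delta-adjusted or reference-based analysis, because the model assumes data are missing at random and the withdrawal grounds make that doubtful.
4. State in Section 9.3 that the week-3 baseline alone does not count as an endpoint measurement for the blinded-phase AUC, or let the model handle such participants. Do not score them as 0.

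The cost is SAP wording, somewhat more analysis work, and reliance on model assumptions at n = 30. No new data are needed, and Section 9.4 already foresees refinement of the analyses before data lock.

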2.4.1.2 Known Potential Benefits

Subjects may or may not directly benefit from being in the study. Close medical monitoring of their symptoms may be a potential benefit if subjects are seen infrequently otherwise. Furthermore, if the medication is effective for tinnitus, participants may indeed improve. However, the overall benefit of participating in this research is that it may help others with tinnitus in the future.

3 Objectives and Purpose

The purpose of this study is to evaluate the effects of high-dose intranasal oxytocin for treating tinnitus.

The primary outcome measurement will be a change in the VAS at 3 timepoints:

1. Comparative endpoint of VAS of all 30 subjects at 9th week of treatment with active drug vs baseline.

2. Comparative endpoint during the cross-over phase of VAS at the 17th visit (15th week of study) between the 15 subjects who received placebo vs the 9th week of the non-blinded phase for the same subjects (when they were on active drug). This endpoint compares the 15 patients that were switched from active to placebo and compares their response on placebo (from the double blind phase) with their response on active drug (from the non-blinded phase) and compares them to the 15 subjects that remained on active drug during the entire study.

3. A parallel group analysis where we compare both arms in the last week of the double-blind phase—so in essence we are comparing those 15 who were on active throughout the entire study to those that started on active and changed over to placebo.

Secondary endpoints of interest are also defined a-priori:

1. A change in the THI by at least one grade contrasting the 9th week (end of the single blinded phase) and the 15th week of the study (end of the double blinded phase) between the 15 subjects who were switched from active drug to placebo.

2. A change in the THI by at least one grade during the last 2 weeks of the double-blind stage (weeks 14 and 15 of the study contrasting those on active drug vs. placebo.

Exploratory endpoints of interest include:

Clinical Global Impression (CGI) measured following the same approach of the primary endpoints. Tinnitus Functional Index (TFI) measured following the same approach of the primary endpoints.

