5.4 Strategies for Recruitment and Retention

We will recruit patients from NYU Langone Medical Center's Departments of Otolaryngology and Neurology. We will aim to recruit and enroll 50 patients with a goal of 30 study participants remaining after accounting for some screen failures. Subjects will be identified for study inclusion through otolaryngologists' and neurologists' referrals of patients with tinnitus.

An IRB-approved dear provider letter will be sent to providers from NYU Departments of Otolaryngology and Neurology to assist in identifying potential study participants for referral to the study team. A member of the study team will contact the individual for screening for the study. Data including patient initials, age, date of birth, menstrual status (if applicable), allergies, prior history of migraine, tinnitus quality, severity, duration, ENT evaluation, and current medications will be used for subject identification, informing subjects, and initial discussion of subject eligibility. Information will be obtained through review of medical records and direct interview. The Principal Investigator will review the informed consent form with the potential participant. The Principal Investigator and Research Coordinator will have access to identifiable information as needed for recruitment of study participants. Emails will be securely sent to potential participants via send safe.

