9.2 Statistical Hypotheses

We hypothesize that treatment with high dose oxytocin nasal spray will result in a large effect size as measured by partial eta squared for the difference in mean area under the curve in baseline adjusted VAS when compared to placebo during the blinded study phase.

The primary outcome measurement will be the collective area under the VAS curve above the week 3 baseline as assessed from week 3 to week 6 of the blinded study phase. The area under the curve will be determined using the linear trapezoidal method for each participant after subtracting the baseline (week 3) VAS value from each subsequent measure to determine the collective improvement/decline of the VAS measurement during the blinded study phase. The mean and standard deviation of the total area will be

calculated for each study arm (active drug and placebo) and partial eta squared effect size for the difference determined. This effect size estimate can then be used to power future comparative studies.

The same area under the curve above the baseline VAS metric will be determined separately for the nonblinded/open label study phase. The inherent bias of non-blinding may influence this metric although the relatively larger sample size (n=30) could also improve precision. Therefore, the area will be presented as a descriptive summary using the mean and standard deviation with an effect size estimate.

Secondary endpoints will consist of safety and tolerability metrics including adverse event incidence and severity, regimen adherence and voluntary study drop-out rates reported during the non-blinded and blinded study phases. The frequency and percentage of each secondary measure will be determined for the non-blinded study phase and by study arm for blinded study phase. Additionally, any changes in THI greater than 1 grade will be determined from week 3 to week 6 of the blinded study phase. The frequency and percentage of these changes will be summarized by study arm.

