9.4.6 Baseline Descriptive Statistics

Descriptive summaries will be performed separately for the non-blinded study phase and by study arm for the blinded study phase using means, standard deviations, and frequencies and percentages. There will be no inferential statistics used as randomization should eliminate the potential for bias.

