9.5 Sample Size

This is a pilot, proof of concept study with the main goal of providing an estimate of the effect size difference between treatment and placebo control. As such the sample size of n=30 will provide sufficient estimates of the effect sizes necessary to power a future two-armed randomized study

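### No arm comparison is covariate-adjusted for a pre-randomisation VAS, and the Week 15 parallel-group comparison names no baseline term, although Week 9 VAS is collected

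*Combined protocol and SAP*

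**What the plan says.** Section 9.4.2 summarises the primary area by arm, "The mean and standard deviation by study arm in the area under the VAS curve from baseline will be presented", together with a partial eta squared for the difference between arms. The hypothesis in Section 9.2 speaks of baseline-adjusted VAS, but the method given there is subtraction: "after subtracting the baseline (week 3) VAS value from each subsequent measure". That value comes from week 3 of the blinded phase ("The week 3 data after two week washout will serve as the baseline"), so it is taken after the randomisation at Visit 11 (Week 9). No covariate, ANCOVA or regression is named anywhere in Section 9.

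Section 3 lists three VAS comparisons as primary outcome measurements. Item 3 is "A parallel group analysis where we compare both arms in the last week of the double-blind phase"; it names no baseline term. Item 2 sets Week 15 on placebo against Week 9 on active drug in the same 15 subjects, then compares them with the arm that stayed on active drug. It gives no model.

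The arms are planned at 15 each: "we are comparing those 15 who were on active throughout the entire study to those that started on active and changed over to placebo". Section 9.5 says "the sample size of n=30 will provide sufficient estimates of the effect sizes necessary to power a future two-armed randomized study". Section 9.6.1.1 describes block randomisation to balance the arms and mentions no stratification by VAS. Section 4.1 has a daily VAS log in the baseline week, and Section 7.2.3.9 has the VAS log reviewed at Visit 11, the randomisation visit.

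**The concern.** The trial's product is an effect size that will be used to power a later trial. At 15 per arm, the arms can differ in VAS at randomisation by chance. An end-of-phase comparison that ignores this carries part of the difference into the estimated treatment effect, in either direction. A change score corrects it with a coefficient fixed at 1, which over-corrects when the correlation is below 1. A fitted coefficient for a pre-randomisation VAS removes the predictable part and lowers the residual variance. The data for this are already collected, so the plan gives up precision for nothing.

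Once an unadjusted effect size has been carried into the next sample size calculation, a chance imbalance can no longer be separated from the effect.

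**Working it through.** **Nothing to reproduce.** Section 9.5 gives n = 30 with no alpha, power, SD or difference. The calculations below only show how much adjustment could matter.

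**Inputs.** From the documents: 15 per arm, randomisation at Week 9, last-week comparison at Week 15. Assumed: SD = 1 at both times; correlation ρ between Week 9 and Week 15 VAS over a range, since none is given; d = 0.8 and two-sided 5% for illustration, since the plan sets no alpha for the primary.

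**Chance imbalance.** The SD of the baseline difference between arms is √(2/15) = 0.365. The probability of an absolute difference above 0.5 SD is 2 × [1 − Φ(0.5/0.365)] = 17%; above 0.3 SD it is 41%. With a 0.5 SD imbalance and ρ = 0.7, a raw Week 15 difference shifts by 0.7 × 0.5 = +0.35 SD, and a change from Week 9 by (0.7 − 1) × 0.5 = −0.15 SD.

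**Week 15 comparison.** The standard error is √[(2/15) × V], with:
- raw values: V = 1
- change from Week 9: V = 2(1 − ρ)
- adjusted for Week 9: V = (1 − ρ²) × 27/26, where 27/26 is the cost of estimating the slope.

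| ρ | SE raw | SE change | SE adjusted |
|---|---|---|---|
| 0.3 | 0.365 | 0.432 | 0.355 |
| 0.5 | 0.365 | 0.365 | 0.322 |
| 0.7 | 0.365 | 0.283 | 0.266 |
| 0.8 | 0.365 | 0.231 | 0.223 |

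A simulation of 40,000 trials at ρ = 0.7 gave 0.364, 0.282 and 0.265, in agreement with the formulas. Adjustment beats the raw comparison once 1 − ρ² < 26/27, that is, above ρ of about 0.19.

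Power from the noncentral t at d = 0.8 on the raw scale: unadjusted, 0.8/0.365 = 2.19 on 28 df gives 56%. Adjusted, on 27 df: 0.8/0.355 = 2.25 gives 58% (ρ 0.3); 0.8/0.322 = 2.48 gives 67% (ρ 0.5); 0.8/0.266 = 3.01 gives 83% (ρ 0.7).

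**Primary area.** Taking weekly values V3 to V6 in the blinded phase, the planned trapezoid is V4 + V5 + 0.5·V6 − 2.5·V3. With equal correlations its variance is 8.5(1 − ρ). The pre-randomisation alternative is the unsubtracted area 0.5·V3 + V4 + V5 + 0.5·V6, adjusted for Week 9, with variance [2.5(1 − ρ) + 9ρ − 9ρ²] × 27/26.

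| ρ | planned | unsubtracted, Week 9-adjusted | ratio |
|---|---|---|---|
| 0.5 | 4.25 | 3.63 | 0.86 |
| 0.7 | 2.55 | 2.74 | 1.08 |
| 0.8 | 1.70 | 2.01 | 1.19 |

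With AR(1) correlation of 0.7 per week the figures are 4.28 planned and 6.28 adjusted. Adding Week 9 as a covariate to the planned, subtracted area also gains nothing under equal correlations: the two are uncorrelated, and the variance at ρ = 0.7 goes from 2.55 to 2.65.

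**The case against.** Several objections stand, and they set the limits of the point.

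- **The primary area.** A reader might infer that adjustment for a pre-randomisation VAS would also sharpen the primary area. The figures above do not support that. Fitting the week 3 coefficient instead of fixing it would lower the variance (2.06 against 2.55 at ρ = 0.7), but week 3 is post-randomisation. Moving the anchor to Week 9 changes the estimand, because it counts any arm difference already present at week 3.
- **Raw values at Week 15.** It is tempting to say that item 3 compares raw values. The documents do not say so. Section 3 introduces its three items as a change in VAS, and Section 9.4.1 speaks of a VAS difference from baseline. Section 9 describes no Week 15 analysis. If a change from Week 9 is meant, the gain is the smaller one.
- **No use of a pre-randomisation value.** That would be too strong. Item 2 uses Week 9 as a reference, though without a model.
- **Section 9.4.6.** The sentence "There will be no inferential statistics used as randomization should eliminate the potential for bias" might be read as a refusal to adjust. It stands under baseline descriptive statistics, and declining significance tests on baseline tables is ordinary practice. It needs no change on this account.
- **A pilot without a primary test.** Power at 5% is not the plan's own criterion, and unadjusted intervals already allow for chance imbalance. That is right, but the standard errors make the same case for an estimate.

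Section 9.4 also says that the analyses will be refined before data lock. It names no adjustment, so it does not fill the gap, and a covariate chosen at that stage would be less credible than one named now.

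**Conclusion.** The point holds for the Week 15 parallel-group comparison. No arm comparison in the plan has covariate adjustment for a pre-randomisation VAS, although one is collected, and item 3 leaves its handling of baseline open. Under either reading of item 3, fitting Week 9 VAS gives the smallest standard error at each correlation tabulated. Against raw values the gain is negligible at ρ = 0.3 and large at 0.7. Against change from Week 9 it is moderate at 0.5 and small at 0.7 and above. These sizes rest on an assumed correlation, equal SDs and 15 evaluable per arm.

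The point does not extend to a precision or power gain for the primary area, where the Week 9-adjusted alternative is less precise than the planned area at ρ of 0.7 or above under equal correlations. No figure stated in the plan is wrong because of this point.

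**What to change.** In Section 3 item 3 and Section 9.4.2, specify that the Week 15 arm difference in VAS is estimated by a linear model with arm and Week 9 (pre-randomisation) VAS. State which log entries make up each value. Report the adjusted difference with its 95% CI and the partial eta squared from that model, and keep the unadjusted means and SDs by arm alongside.

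Leave the primary area as defined for this purpose. An unsubtracted area adjusted for Week 9 may be added only as a sensitivity analysis, labelled as a different estimand.

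The cost is SAP wording and one degree of freedom, with no new data. The one drawback is that an adjusted partial eta squared is not on the same scale as an unadjusted one, so both should be shown and labelled, particularly for whoever uses them to size the next trial.
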